Patients with stage IV and V chronic kidney disease and end stage renal disease requiring hemodialysis at UAB Dialysis Clinics will be recruited from the UAB Vascular Access Clinic, which has been the site for recruitment of patients requiring new vascular access for the last 10 years.

3. Inclusion/Exclusion Criteria:

Inclusion Criteria:

1. Age ≥ 19 years of age male or female
2. Chronic Kidney Disease Stage IV or V patients or End Stage Renal Disease Patient requiring arteriovenous fistula surgery

Exclusion Criteria:

1. Patient currently on nitrate therapy or any nitric oxide donor in any form
2. Patient currently on protease inhibitor or non-nucleoside reverse transcriptase inhibitor
3. Patient with resting systolic blood pressure < 90 mm Hg and diastolic blood pressure < 50 mm Hg.
4. Patient life expectancy < 9 months.
5. Patient unable or unwilling to meet study requirements.

4. Randomization Process:

Sildenafil will be purchased and obtained by the UAB pharmacy. The pharmacy will over-encapsulate the Sildenafil tablets to match a placebo encapsulated tablet.

The first subject recruited will be unblinded and receive Sildenafil. After the first subject, all subsequent subjects will begin the randomization process.

Randomization Process: Subjects agreeing to this study will be randomized at the 1st vascular function testing visit. 20 numbers generated by a biostatistician will be randomly assigned numbers to the Sildenafil treatment group (10 numbers) and randomly assigned to the placebo (10 numbers). The investigators and clinical coordinators will be unblinded to the treatment group of the subject and have access to the randomization assignments.

1. Treatment/Intervention Group: 10 patients will take Sildenafil 20 mg twice a day oral from the time after randomization (1st vascular test visit) until the 2 weeks post-operative arteriovenous fistula ultrasound.

2. Placebo Group: 10 patients will take placebo twice a day oral from the time after randomization (1st vascular test visit) until the 2 weeks post-operative arteriovenous fistula ultrasound.

5. Procedures and Study Visits:

Study Procedures:

Randomization will occur at the time of the 1st vascular function testing. The first subject will be unrandomized and receive Sildenafil. Subsequent subjects will be randomized to receive either

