Sildenafil 20mg twice a day or placebo twice a day, based on randomization scheme. Subjects will begin either placebo or Sildenafil after randomization during the first vascular function visit until the 2 weeks postoperative arteriovenous fistula ultrasound.

Enrolled subjects will have an initial brachial artery flow-mediated dilation (FMD) and venous plethysmography (VP) studies performed approximately 2 weeks prior to scheduled AVF creation and a subsequent FMD and VP study prior to surgery. The FMD and VP studies are non-invasive studies. Completion of these studies will take approximately 3-4 hours.

Up to four teaspoons of blood will be drawn at the 1st FMD/VP study prior and second FMD/VP study. Blood samples will be obtained using the standard method used to obtain blood for routine hospital tests. Completion of blood draw will take approximately 10-15 minutes.

Pre-operative, 2 weeks and 6 weeks post-operative ultrasounds will be performed on participants. The pre-operative and 6 week ultrasounds are part of standard medical care and will be performed whether the participant is in the study or not.

Discarded vein and artery specimens (approximately 5-10 mm each) will be collected at the time of AVF surgery. This procedure requires 3-5 minutes, and does not affect surgical outcome.

A total of 21 subjects will be recruited for this study with prospective follow-up. The first patient will be unblinded and receive the drug. Subsequently, 10 subjects will be randomized to receive 20 mg of Sildenafil twice a day oral and 10 patients randomized to receive placebo twice a day oral. Information related to demographics, comorbidities, and AVF outcome following surgery will be collected. The primary clinical endpoint is change in baseline and 2 week FMD/VP measurements. The secondary outcome is change in blood flow and vein and artery diameters at 2 and 6 weeks.

Study Visits:

Visit 1: Screening and enrollment 1-2 hours (Research)

- Informed consent
- The study team will determine qualification to participate in this study

Visit 2: Baseline Visit (in some cases Visit 1 and 2 could be combined) (Research)

- Detailed medical history
- Height and weight measured
- Blood draw (in some cases this could occur in the dialysis unit)

Visit 3: 1st Vascular Function Test and Pre-operative Ultrasound

- Vascular Ultrasound (Standard care)
- Vascular Function Testing (3-4 hours)
 - Brachial artery flow mediated vasodilation and venous plethysmography (Research)

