July 11, 2018

[name], Principal Investigator
University of Alabama at Birmingham
Birmingham, AL 35294

The data will be analyzed in two stages: (1) descriptive statistics, which will include means and standard deviations for normally distributed continuous variables, medians and interquartile ranges for skewed continuous variables, and proportions for categorical measures and (2) two-group t test, Wilcoxon rank-sum tests, chi-square tests, and simple logistic regression and multiple logistic regression modeling. P values <0.05 will be considered statistically significant.

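### Does the unrandomized first subject on sildenafil end up in the between-group comparison?

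*Combined protocol and SAP*

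**What the plan says.** Three places mention the first subject. Section 4 (Randomization Process) says "The first subject recruited will be unblinded and receive Sildenafil", with randomization starting after that person. Section 5 (Procedures and Study Visits) repeats it: "The first subject will be unrandomized and receive Sildenafil". Later in Section 5, beside the sample size ("A total of 21 subjects will be recruited for this study with prospective follow-up"), comes "The first patient will be unblinded and receive the drug".

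The randomized part is described separately. Section 4 has a biostatistician generate 20 numbers, 10 for each arm, and defines the active group thus: "10 patients will take Sildenafil 20 mg twice a day oral from the time after randomization". The placebo group is defined in the same way, also with 10 patients. Section 5 agrees: "Subsequently, 10 subjects will be randomized to receive 20 mg of Sildenafil twice a day oral and 10 patients randomized to receive placebo".

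The SAP is one paragraph. It opens "The data will be analyzed in two stages", lists descriptive statistics and then two-group tests and logistic regression, and sets significance at P < 0.05. It names no analysis population and does not mention the first subject.

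**The concern.** The first subject's treatment is fixed by order of recruitment, is known, and can only be sildenafil. Section 5 describes the vascular function tests, blood draws and ultrasounds for enrolled subjects without excepting this person, so primary and secondary endpoint data will exist. Because the SAP speaks only of the data, an analyst could put this subject in the sildenafil arm and compare 11 with 10.

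Two things would then be at stake. The comparison would no longer rest wholly on randomization, and any departure of this subject from the others would fall on the active side alone. Also, if the choice between 10 versus 10 and 11 versus 10 were left until results were visible, it could be made in favor of the better-looking answer.

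**Working it through.** **Inputs from the documents.** One unrandomized subject on sildenafil (Sections 4 and 5); 10 randomized to sildenafil and 10 to placebo (Sections 4 and 5); 21 in total (Section 5); two-group tests at 0.05 (SAP).

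**Assumptions.** The documents give no SD, effect size or power. I assume normal data with equal variances, a two-sided t test, 80% power where power is needed, and a first subject whose change lies k SD from the expected mean of the other sildenafil subjects, with k from 0 to 3.

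**Step 1: the stated total.** 1 + 10 + 10 = 21, which reproduces the protocol's figure. The first subject is in the recruitment count.

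**Step 2: which groups the two-group tests compare.** The SAP does not define the groups, so the definitions must come from the protocol.

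- Section 4, active group: 10 patients, dosed after randomization. The first subject is not randomized and does not meet this definition.
- Section 4, placebo group: 10 patients, same wording.
- Section 4, allocation: 20 numbers, 10 per arm. The first subject has none of them.
- Section 5: the first patient is listed, and the 10 and 10 come subsequently.

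No place describes a sildenafil group of 11. The protocol's definitions give 10 versus 10.

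**Step 3: size of the effect if the subject were pooled anyway.**

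- Weight in the arm: 1/11 = 9.1%. Share of all subjects: 1/21 = 4.8%.
- Shift in the difference: k/11 SD.
- Standard error of the difference: sqrt(1/11 + 1/10) = 0.437 SD.

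| k (assumed) | Shift, SD | Shift, standard errors |
|---|---|---|
| 0 | 0 | 0 |
| 1 | 0.09 | 0.09/0.437 = 0.21 |
| 2 | 0.18 | 0.18/0.437 = 0.42 |
| 3 | 0.27 | 0.27/0.437 = 0.62 |

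**Step 4: type I error if pooled (400,000 simulated trials per k).** Two-sided rejection under the null is 4.9%, 5.0%, 4.7% and 4.4% for k = 0, 1, 2 and 3. If the departure favors sildenafil, the part of that error pointing toward sildenafil is 2.5%, 3.6%, 4.1% and 4.2%.

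**Step 5: what inclusion would buy.** The difference detectable with 80% power is 1.32 SD at 10 versus 10 and 1.29 SD at 11 versus 10. The gain is 0.03 SD, so an analyst has almost no incentive to pool.

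**The case for a change.** The strongest reply is that the 10 and 10 in Section 4 are allocation counts, not an analysis population. The SAP does not refer back to them, so two analysts could claim to follow the plan and produce different comparisons. The near-nominal two-sided error also hides an imbalance: with a first subject 2 SD in sildenafil's favor, false positives toward sildenafil rise from 2.5% to 4.1% while those toward placebo fall below 1%. If someone reported whichever of the two analyses was significant, the two-sided error would be 6.0% with no departure and 6.7% at 2 SD. Section 4 also leaves investigators and coordinators unblinded with access to the assignments, so such a choice could be an informed one.

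The arithmetic stands, and so does the observation that the SAP never writes the exclusion down. But each of these effects needs a step the plan does not call for: putting an unrandomized person into a group defined as randomized, or running both versions and choosing between them. The staff's knowledge of assignments covers all the subjects and would be unchanged by anything said about the first one. The subject's own knowledge of treatment is also a weaker route to bias here, because the primary endpoint is a vascular measurement and not a self-report.

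**Conclusion.** The concern does not call for a change. The plan nowhere says that the first subject is pooled with the sildenafil arm, and the only group definitions it contains leave that subject out. An analyst using them would compare the 20 randomized subjects, 10 with 10, and describe the first one separately. The SAP's silence is a gap that ordinary practice fills.

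A contrary reading would have a modest effect: at most 0.27 SD, or 0.62 standard errors, for a subject as far as 3 SD from the rest, with overall two-sided error no higher than about 5% for a single pooled analysis. These sizes rest on the assumed 0 to 3 SD range and on normal data with equal variances, since the documents supply no variability figures. The conclusion that the comparison is 10 versus 10 does not depend on those assumptions. It rests on Sections 4 and 5 of the protocol.

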- Blood draw (if not collected during visit 2) (Research)
- Randomization to either study drug Sildenafil or placebo

Visit 4: 2nd Vascular Function Test

- Vascular Function Testing (3-4 hours)
 - Brachial artery flow mediated vasodilation and venous plethysmography (Research)

Visit 5: Arteriovenous Fistula Surgery

- Fistula creation (Standard care)
- Discarded vein and artery tissue collection (Research)

Visit 6: 2 Weeks Post-Operative Ultrasound

- Vascular Ultrasound (Research)

Procedures and Length of Time:

Procedure	Length of Time Required of Participants	Frequency of Repetition	Research (Res) – OR- Routine Care
Blood Drawing	10-15 minutes	Baseline Visit Week 2	 Res  Routine  Res  Routine
Height and Weight	5 minutes	Baseline visit	 Res  Routine
Taking Sildenafil 20 mg or Placebo bid oral	2 minutes	Daily from the time after randomization (1st vascular test visit) until the 2 weeks post-operative arteriovenous fistula ultrasound	 Res  Routine
Vascular Function Testing –FMD and VP	3-4hrs	Pre-operatively at baseline Two weeks after baseline	 Res  Routine  Res  Routine
Vascular Ultrasound	1-2hrs	Pre-operative Week 2 Visit Week 6 Visit	 Res  Routine  Res  Routine  Res  Routine

Discarded Vein and Artery Tissue Collection	3-5 minutes of surgery time	Once	 Res  Routine

6. Length of Time of Follow-up and Subject Participation:

Total Follow-up Time: 2 years to follow clinical data related to clinical survival of the fistula.

Total Participant Time: Up until the six week postoperative ultrasound.

**Phosphodiesterase Type 5 Inhibition to Improve
Endothelial Function and Vascular Remodeling in
Chronic Kidney Disease and End Stage Renal Disease
Patients Requiring New Arteriovenous Fistula**

Statistical Analysis Plan

NCT Number: NCT02414204

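### The secondary outcome does not say what change in blood flow is measured from or in which vessel; compare attained values at weeks 2 and 6, adjusted for pre-operative diameter

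*Combined protocol and SAP*

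**What the plan says.** Protocol section 5 (Study Procedures) defines the outcome in one sentence: "The secondary outcome is change in blood flow and vein and artery diameters at 2 and 6 weeks". It gives no reference time for the change and no vessel or site for the flow.

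The scans available are set out in the same section: "Pre-operative, 2 weeks and 6 weeks post-operative ultrasounds will be performed on participants". The visit list places the first of these at "Visit 3: 1st Vascular Function Test and Pre-operative Ultrasound", where the last item is "Randomization to either study drug Sildenafil or placebo". On dosing, the section says: "Subjects will begin either placebo or Sildenafil after randomization during the first vascular function visit until the 2 weeks postoperative arteriovenous fistula ultrasound". The first vascular function study is "performed approximately 2 weeks prior to scheduled AVF creation". The fistula is made at Visit 5, and its first scan is "Visit 6: 2 Weeks Post-Operative Ultrasound".

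The SAP is one paragraph. For continuous outcomes it names the two-group t test and the Wilcoxon rank-sum test. Its only regression models are logistic. It defines no baseline, no change score and no covariate for a continuous outcome.

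**The concern.** The sentence joins two kinds of measurement. Artery and vein diameters exist before and after surgery, so a change from the pre-operative scan is well defined. Fistula flow does not exist until Visit 5. An analyst who takes blood flow to mean fistula flow has two ways to form a change: subtract a native-vessel flow from the pre-operative scan, if one was recorded, or subtract the week-2 fistula flow from the week-6 value.

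The second way subtracts a value taken at the end of treatment. Any benefit already gained by week 2 is removed from the comparison, and the interval that remains lies wholly after study drug has stopped. A benefit that is kept would appear as no difference, and one that is partly kept would appear as harm.

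Because the reference is open, it could also be settled after the data are seen, in a trial where section 4 gives investigators and coordinators access to the assignments.

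**Working it through.** **Plan's own figures.** The total is 1 + 10 + 10 = 21, which agrees with section 5. No effect size, SD, correlation or power is given for any outcome, so there is no power figure to reproduce.

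**Timeline (from the documents).** Drug starts about 2 weeks before surgery and runs "until the 2 weeks post-operative arteriovenous fistula ultrasound". The first fistula reading therefore follows about 2 + 2 = 4 weeks of assigned treatment. It is a post-treatment value. The pre-operative scan is listed ahead of randomization at Visit 3 and so precedes drug.

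**What each reference estimates.** Let D2 and D6 be the true between-arm differences in fistula flow at weeks 2 and 6.
- Attained value: D2 at week 2, D6 at week 6.
- Change from the pre-operative scan: the arms have the same expected pre-operative value, so the contrast is again D2 and D6. There is no bias.
- Change from week 2 to week 6: D6 − D2. This is zero if D6 = D2 and negative if 0 < D6 < D2.

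**Size if the week 2-to-6 change were used.** From the documents: 10 randomized per arm, significance at 0.05. Assumed: two-sided test, equal SDs (set to 1), normal data, correlation r between weeks 2 and 6 of 0.3 to 0.7, and the effects below. With 18 degrees of freedom the critical t is 2.101. The noncentrality is d × √(10/2) = 2.236d.

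- *Benefit of 1.32 SD at both weeks.* On the week-6 level, noncentrality is 1.32 × 2.236 = 2.95 and power is 79.7%. On the change, the expected difference is 0, so a significant result occurs in 2.5% of trials in each direction.
- *Benefit of 1.32 SD at week 2 and 0.66 SD at week 6.* The expected difference in change is 0.66 − 1.32 = −0.66, and the SD of the change is √(2 − 2r):

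| r | SD of change | Standardized difference | Noncentrality | Significant against drug |
|---|---|---|---|---|
| 0.3 | 1.183 | −0.558 | −1.247 | 21.8% |
| 0.5 | 1.000 | −0.660 | −1.476 | 28.7% |
| 0.7 | 0.775 | −0.852 | −1.905 | 43.8% |

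**Sensitivity to the assumptions.** A simulation of 40,000 trials per case used other assumed values: placebo flow 600 then 750 mL/min, SD 250, r of 0.5 or 0.8, and pre-operative native flow 50 with SD 20.
- Gain of 200 at week 2, 100 left at week 6: the week 2-to-6 change is significant against drug in 13% (r = 0.5) to 27% (r = 0.8).
- Gain of 200 at week 6 only: the change favours drug in 40% to 76%, against 40% for attained flow, so it does not mislead.
- Gain of 200 at both weeks, with the pre-operative native value as reference: 39%, against 40% for attained flow.

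**Gain from adjustment, diameters.** With equal SDs before and after and pre-to-post correlation r, the change score has variance 2 − 2r and ANCOVA has residual variance 1 − r². The ratio is (1 − r²)/(2 − 2r) = (1 + r)/2:
- r = 0.3: 0.91/1.40 = 0.65
- r = 0.5: 0.75/1.00 = 0.75
- r = 0.7: 0.51/0.60 = 0.85

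**The case against.** The strongest reply is that the plan does not contain the harmful reading, and that its wording points away from it. A change reported at 2 weeks as well as at 6 needs an earlier reference, and the only earlier ultrasound is the pre-operative one. The same sentence covers diameters, for which that scan is the obvious baseline. This stands, and it limits the point in three ways.

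- A reader might infer that blood flow has no valid starting value at all. The documents do not support that. They never say that blood flow means fistula flow, and a native-vessel flow taken before drug would be a legitimate, unbiased reference. Whether the scan records flow is simply not stated.
- A reader might infer that the planned analysis will hide or reverse a benefit. That follows only if week 2 is taken as the starting value, which the plan does not say. With the pre-operative reference nothing is hidden or reversed.
- A reader might infer that subtracting a native-vessel flow must add serious noise. The variance of the change relative to the attained value is 1 + k² − 2rk, where k is the ratio of the pre-operative SD to the fistula-flow SD and r is here the correlation between those two flows. At k = 20/250 = 0.08 and r = 0 it rises by 0.6%. At k = 0.25 and r = 0.5 it falls by about 19% (1 + 0.0625 − 0.25 = 0.8125). Without figures in the documents, even the direction is unknown.

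It is also fair to say that no error is shown for change in diameter, and that this is one part of a secondary outcome in a study of 21 subjects. What the reply does not remove is that the reference and vessel are unstated, that one possible reading is invalid, and that the SAP leaves the pre-operative measurement unused as a covariate.

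**Conclusion.** The point holds as an undefined reference and site for change in blood flow, together with an inexpensive improvement in the analysis. It is not a demonstrated bias in the plan.

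The timeline rests on the documents alone: week 2 cannot serve as a baseline for fistula flow. The 22% to 44% of trials significant in the wrong direction is conditional on the week 2-to-6 reading, on the assumed effects of 1.32 and 0.66 SD, and on correlations of 0.3 to 0.7. Other assumed inputs gave 13% to 27%, and a gain appearing only at week 6 gave no distortion.

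For diameters, change from the pre-operative scan is already unbiased. Adjustment there is a gain in precision: 15% to 35% less residual variance than the change score for r from 0.7 down to 0.3, assuming equal SDs and before the one degree of freedom spent on the covariate. For flow, the gain from adjusting for a pre-operative diameter depends on a correlation that the documents do not give, so I put no figure on it.

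**What to change.** Replace the outcome sentence in the protocol, and add to the SAP, wording to this effect: fistula blood flow, vein diameter and artery diameter are compared between the randomized arms as attained values at week 2 and at week 6, each by ANCOVA with the pre-operative diameter as covariate. Use the matching diameter for each diameter outcome. For flow, name in advance either the pre-operative artery or the pre-operative vein diameter. State that the week-2 value is not used as a baseline.

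The cost is one sentence and one covariate per model (18 residual degrees of freedom become 17 with 20 randomized patients). The SAP must add a linear model for continuous outcomes, which it does not now list. No new measurement is needed, because the pre-operative ultrasound is already scheduled as standard care.

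### Change in FMD/VP uses baseline with its slope fixed at 1; no analysis listed in the SAP estimates that slope, and a baseline-adjusted linear model would be a cheap, optional gain in precision

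*Combined protocol and SAP*

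**What the plan says.** Protocol section 5 (Procedures and Study Visits) defines the endpoint: "The primary clinical endpoint is change in baseline and 2 week FMD/VP measurements". The first test comes before treatment: "Subjects will begin either placebo or Sildenafil after randomization during the first vascular function visit", and the visit list puts vascular testing ahead of randomization at Visit 3. The table of procedures times the two tests as "Pre-operatively at baseline" and "Two weeks after baseline". Every randomized patient is therefore due to have a pre-treatment value of the outcome itself.

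The SAP is one paragraph. Its comparative methods are "two-group t test, Wilcoxon rank-sum tests, chi-square tests, and simple logistic regression and multiple logistic regression modeling". It assigns no method to any endpoint and names no covariates and no linear model. Its descriptive part foresees non-normal data ("medians and interquartile ranges for skewed continuous variables").

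Twenty patients are randomized, 10 per arm. One further patient is treated outside the randomization: "The first patient will be unblinded and receive the drug".

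**The concern.** Of the listed methods, only the two-group t test and the rank-sum test can compare a continuous outcome between arms. Chi-square tests and logistic models need a categorical outcome. The natural reading, though the SAP does not state it, is a t or rank-sum test on each patient's change.

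Subtracting baseline is the right correction only if a 1-unit difference in baseline carries forward as a 1-unit difference at 2 weeks. If the true slope is below 1, subtraction over-corrects. It then adds noise, and it leaves the estimate dependent on any chance difference in baseline means. Randomization keeps the estimate unbiased on average, but with 10 per arm the difference in any one trial can be material. What is at stake is some power in a small trial, using measurements that are collected anyway.

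**Working it through.** **The plan's own figure.** The documents contain no power calculation. The one figure that can be checked is the total: 1 + 10 + 10 = 21, which agrees with section 5.

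**Inputs from the documents.** 10 per arm; significance at 0.05; one pre-treatment and one 2-week value.

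**Inputs assumed.** Two-sided testing, normal data, a true effect of 1 baseline SD, correlation rho from 0.3 to 0.9, and a 2-week SD equal to k times the baseline SD. None of these is in the documents.

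**Chance imbalance.** The difference in baseline means has SD √(2/10) = 0.447 baseline SDs. For a given imbalance, the expected effect on change is shifted by (slope − 1) × imbalance. With slope 0.5, an imbalance of 0.447 shifts it by 0.5 × 0.447 = 0.22 SD, in the direction opposite to the imbalance.

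**Variance.** In units of the baseline variance, and apart from the common factor 2/n (n patients per arm), with N completers:
- t test on change: k² + 1 − 2k·rho
- linear model with baseline as covariate (ANCOVA): k²(1 − rho²) × (N − 3)/(N − 4). The last factor is the expected cost of estimating the slope, 17/16 for N = 20.

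Examples with N = 20:
- k = 1, rho = 0.5: change 1 + 1 − 1 = 1.00; ANCOVA 0.75 × 1.0625 = 0.797; ratio 0.80.
- k = 1.25, rho = 0.8 (slope k·rho = 1): change 1.5625 + 1 − 2 = 0.5625; ANCOVA 1.5625 × 0.36 × 1.0625 = 0.598; ratio 1.06.

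**Power.** Noncentral t, with 18 error degrees of freedom for change and 17 for ANCOVA, the latter averaged over baseline imbalance. For change at k = 1, rho = 0.5, the noncentrality is 1/√(0.2 × 1.00) = 2.24, which gives 56.2%. In the power columns the first figure is the test on change and the second is ANCOVA.

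| rho | Variance ratio, k = 1 | Power, k = 1 | Variance ratio, k = 1.25 | Power, k = 1.25 |
|---|---|---|---|---|
| 0.3 | 0.69 | 43.2 → 57.5% | 0.83 | 34.9 → 40.6% |
| 0.5 | 0.80 | 56.2 → 65.8% | 0.95 | 45.5 → 47.4% |
| 0.7 | 0.90 | 77.9 → 81.7% | 1.04 | 65.1 → 63.2% |
| 0.8 | 0.96 | 91.6 → 92.5% | 1.06 | 80.5 → 77.9% |
| 0.9 | 1.01 | 99.7 → 99.6% | 1.01 | 96.6 → 96.2% |

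**Break-even on variance.** With equal SDs, ANCOVA is more precise below rho 0.88. With k = 1.25, change is more precise from rho 0.60 to 0.91. With k = 0.8, ANCOVA is better throughout (63.6 → 83.9% at rho 0.5). The worst case is a slope of exactly 1, where the variance ratio is 17/16 = 1.0625.

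**With 16 completers.** The cap is 13/12 = 1.083. At k = 1, rho = 0.5, power goes from 46.1 to 54.1%. At k = 1.25, rho = 0.8, it goes from 69.9 to 66.2%.

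**Skewed data.** Assume lognormal values with log SD 0.8 and a multiplicative effect of 1 log SD. Simulated power at rho 0.7 is 74.2% for the rank-sum test on raw change, 63.0% for ANCOVA on raw values and 81.7% for ANCOVA on logs. On the log scale this is the k = 1 setting above, so a t test on log change has 77.9% (simulation gives 77.4 to 77.8%). Of the 7.5 points between 74.2 and 81.7, 3.7 come from moving to a t test on logs and 3.8 from the covariate.

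**The case against.** The strongest reply is that nothing here is an error. The endpoint is defined as a change, a test on change answers it, and baseline is already used. That stands. A reader might infer from the missing covariate model that the plan ignores baseline, or that its comparison is biased or invalid. The documents support neither: section 5 builds baseline into the endpoint, and the arms are randomized.

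The second reply is that the gain rests wholly on assumed values. That also stands. The 14-point gain needs rho 0.3 with equal SDs, and over part of the range shown ANCOVA loses. FMD and VP may differ in correlation and SD ratio, so one measure could gain while the other loses slightly. A reader might infer that adjustment always adds precision; it does not. What survives is the asymmetry: the variance cost is capped at about 6% with 20 completers, whereas the variance reduction reaches 31% at rho 0.3 with equal SDs.

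The third reply concerns skewness. It would be wrong to credit the covariate with the whole advantage of a log-scale model over the rank-sum test, because about half of it at rho 0.7 comes from moving to a t test on logs. An untransformed linear model can do clearly worse than the rank-sum test on skewed data. A covariate model on ranks is no safe default either: in the same simulations it falls just below the rank-sum test on change at rho 0.8 and 0.9 (86.4 against 87.1%; 97.4 against 98.2%). A rule to switch models if data look skewed would leave the primary model open to choice, and section 4 gives investigators access to the assignments. The scale must therefore be fixed in advance.

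Finally, naming a test on change would by itself close the gap that no method is assigned to the endpoint. True, but it would keep the slope fixed at 1.

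**Conclusion.** The point holds as an optional, cheap improvement for FMD and VP only. The planned endpoint uses baseline with a fixed slope of 1, and no listed method can estimate the slope for these continuous measures. A t or rank-sum test on change, which is itself an inferred reading of the SAP, remains valid.

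Under the stated assumptions, with 10 per arm and equal SDs, baseline adjustment adds about 14, 10, 4 and 1 points of power at rho 0.3, 0.5, 0.7 and 0.8, and nothing at 0.9. With a 2-week SD 1.25 times baseline, it adds about 2 points at rho 0.5 and costs 2 to 3 points at 0.7 to 0.8. Since the documents give no SD, correlation or effect size, they do not show which case applies. Confidence is medium. No claim is made about the ultrasound endpoints.

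**What to change.** State in the SAP that, among the 20 randomized patients, the primary analysis of FMD and of VP is a linear model of the 2-week value on randomized group, with the baseline value of the same measure as covariate, reporting the adjusted difference and its 95% confidence interval. Fix the scale (raw or log) for each measure before any outcome data are compared by group, and do not let a judgement of skewness decide it; a log scale requires positive values. Report the t test and the rank-sum test on change as sensitivity analyses. Describe the first, non-randomized patient separately.

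The cost is one SAP paragraph and no new data. The analysis gives up one residual degree of freedom (17 instead of 18). The variance increase is at most about 6% with 20 completers, or about 8% with 16. The largest power loss among the k = 1.25 cases computed is 2.6 points with 20 completers and 3.7 with 16. The primary result would also rest on a linear model in a small sample, which is why the tests on change should stay in the report.
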